However, to our knowledge, no clinical trial has demonstrated the efficacy of such a comprehensive, integrative medicine approach to improve chemotherapy efficacy and quality of life in ALL patients during intensive therapy, let alone any pediatric cancer population. Given the importance of successful induction therapy in predicting long term survival and the negative role of obesity on treatment success, we are proposing a complete personalized dietary and exercise intervention for pediatric ALL patients that aims to reduce fat gained during induction therapy, thereby improving their treatment response and also quality of life.

EXPERIMENTAL DESIGN SCHEMA

1.0 GOALS AND OBJECTIVES

1.1 Hypothesis:

In pre-adolescents, adolescents, and young adults (AYA) diagnosed with NCI/Rome High-Risk B-precursor acute lymphoblastic leukemia (HR-ALL), reducing gains in adiposity (i.e. fat mass) will improve leukemia sensitivity to induction chemotherapy, reduce post-induction minimal residual disease (MRD), reduce fatigue and obesity-associated toxicities, and improve quality of life.

1.2 Primary aim:

In AYA patients newly diagnosed with HR-ALL, to quantify the impact of a personalized dietary and activity intervention to mitigate chemotherapy-induced body fat gain throughout the critical first month of treatment ("induction").

1.3 Secondary aims:

In AYA subjects newly diagnosed with HR-ALL:

1. To compare the rate of leukemia "positive" minimal residual disease (MRD) in the bone marrow at end of induction ($\geq 0.01\%$ mononuclear cells) in those who received the intervention as compared to a historical controls.
2. To assess adherence to, and feasibility of, implementing a personalized and comprehensive dietary and exercise intervention during the first month of intensive chemotherapy

1.4. Exploratory aims:

In AYA subjects newly diagnosed with HR-ALL:

1. To evaluate persistence or extinguishing of this effect over months of continued dose-intensive pre-Maintenance phases of chemotherapy
2. To characterize the direct impact as compared to baseline of the intervention on self- and family- reported quality of life (QOL) outcomes including fatigue, mood, social interaction, and cognitive impairment reported via the PedsQL questionnaire and Child and Adolescent Scale of Participation (CASP) following the induction phase and serially during dose-intensive phases of chemotherapy.
3. To quantify the effect of adiposity on the activity of leukemogenic JAK2/STAT3, PIK3K/AKT/mTOR, MAPK/ERK, and other signaling pathways in leukemia cells as determined by kinase phosphorylation.
4. To quantify the effect of adiposity and of the intervention on the metabolic activity of leukemia blasts and of adipocytes as assessed by IGF-1, other obesity-associated cytokine signaling pathways, adiponectin, leptin, free fatty acid synthesis and metabolism, and levels oxidative stress.

2.0 BACKGROUND AND SIGNIFICANCE

2.1 INTRODUCTION

Obesity is a major cause of morbidity and mortality in the U.S. and worldwide. We and others have shown that obesity increases the risk of cancers such as leukemia, and can impair leukemia treatment and patient survival (1-3). In adults treated for breast and colorectal cancer, altering nutritional intake and increasing physical activity during treatment improves efficacy (4,5) while limiting treatment symptoms like fat gain and fatigue (6). In this proposed study, we will explore how a dieting and exercise intervention throughout the first month of treatment may counteract the adverse impact of body fat on leukemia therapy efficacy, toxicity, and quality of life.

2.2 FAT MASS AND ALL

Obesity increases the incidence of many cancer types, and obese cancer patients have a higher risk of mortality from their disease (3). In 2007, a landmark study in the Children's Oncology Group (COG) led by [name] from the Children's Hospital Los Angeles (CHLA) demonstrated in two large cohorts (4,314 and 1,160 patients) that obesity at the time of diagnosis increases risk of relapse in children with National Cancer Institute/Rome High-Risk B-precursor ALL (HR-ALL) by 50% (1), a finding independently confirmed in a different population of children (7) in obese adults (8), and by meta-analysis (2). In a recent study, 36% of children with ALL were overweight or obese at diagnosis (9), while in another cohort 23% of children with HR-ALL continued to be obese throughout therapy (10). In our earlier cohort of adolescent and young adults with HR-ALL treated at CHLA, we found an even higher prevalence of high body fat whereas 48% were overweight or obese at diagnosis. Our data also showed that all individuals – both those lean and those obese- gain a significant amount of adipose tissue during the first month of treatment alone ("induction"). On average, patients gained ~20-30% of fat above their starting body fat percentage. The use of glucocorticoids such as dexamethasone and prednisone during induction therapy likely contribute to this fat gain, as they stimulate adipogenesis and appetite. Predisposition to inactivity due to intensive leukemia treatment combined with steroid-induced dietary derangements are therefore likely moderating factors of this marked gain in body fat. As response to leukemia treatment in the first month of therapy is a key determinant of overall prognosis and risk for relapse, and as obesity and body fat are risks factors for relapse, an intervention aimed at reducing the gain in body fat has potential to improve leukemia therapy efficacy starting from the initial time of diagnosis.

2.3 DIETING, ACTIVITY AND CANCER

The concept of introducing caloric restriction in animal cancer models has been explored throughout the last century (11). Recent experiments have focused on the theory of "differential stress resistance," a diet restrictive metabolic state that increases normal tissue, but not cancer cell, tolerance to chemotherapy (12). During carcinogenesis, cancer cells acquire mutations to various metabolic oncogenes, such as Akt and Ras, which allow uncontrolled proliferation. During dietary restriction and the subsequent lack of nutrients and growth factors, normal cells down-regulate their metabolic activity while cancer cells

maintain their elevated metabolic state, a condition that promotes greater chemotherapy specificity toward cancer cells. This was demonstrated in a transgenic mice with human neuroblastoma fasted for 48 hours prior to etoposide treatment. The fasted mice not only survived longer than non-fasted mice but also suffered less drug-induced toxicity (13).

While such a severe starvation diet is not feasible in the clinical setting, altering dietary composition and/or reducing caloric intake is sufficient to see similar results. In a murine prostate cancer model, mice fed with either a low-fat or no-carbohydrate diet had significantly reduced tumor growth compared to mice on a “Western” diet (14). Similarly, a low carbohydrate, high protein, isocaloric diet limited squamous cell carcinoma and breast cancer growth in mice (14). Even restricting total caloric intake during treatment by 30% regardless of dietary makeup reduced breast tumor aggressiveness and tumoral fat content (15). Our own preliminary research (described below) has demonstrated a similar effect of caloric and fat restriction on reducing weight and improving survival of obese mice with ALL.

Physical activity during therapy has also been shown efficacious to augment cancer sensitivity. Mice that were allowed to run on a wheel had slower breast tumor growth and improved immune function compared to non-exercised mice (16). Furthermore, the amount of running inversely correlated with the size of the tumor. Similarly, serum from men who exercise for one hour prevented prostate cancer growth *in vitro* compared to cells in serum from non-exercising men (17). Despite this history and the breadth of research into diet and exercise interventions as adjuvants to chemotherapy, the translation of these laboratory findings into the clinical setting has remained a barrier.

Diet and exercise have concrete benefits in addition to potentially augmenting chemotherapy efficacy. Multiple clinical trials conducted in the last ten years have demonstrated the ability of diet and/or exercise to prevent chemotherapy-associated fat gain, reduce fatigue and improve emotional well-being in adults with solid tissue and hematological cancers (5, 18, 19). Furthermore, the American Cancer Society has recommended that proper nutrition and physical activity play a role in all phases of cancer treatment (20).

2.4 DIET AND ACTIVITY INTERVENTIONS FOR OBESITY

With 16.9% of 2-19 year olds being obese (21) and at risk for serious co-morbidities (22), there is a necessity for effective obesity-targeted pediatric interventions. While many interventions have long existed for obese adults, their efficacy in obese children has only begun to be explored recently. Obese children without cancer randomized to an intervention prescribing 90 minutes of moderate exercise three times per week, a hypocaloric diet, and weekly meetings with a dietitian had a lower BMI, body fat percentage and LDL cholesterol level than children receiving only individual diet or exercise (23). Similarly, a 16 week low-carbohydrate plus aerobic and strength training intervention proved more effective in reducing BMI, body fat and fasting glucose compared to diet or exercise alone (24).

2.5 QUALITY OF LIFE DURING ALL THERAPY

As the treatment for ALL has become more successful, the assessment and improvement of patient QOL are becoming the focus for new studies and treatment modalities. To date, multiple assessment tools

have been developed to assess QOL in the pediatric cancer population. One such tool, the Pediatric Quality of Life Inventory (PedsQL), in conjunction with the PedsQL 3.0 Fatigue Module, has been shown to be particularly effective in assessing physical, emotional and social functioning, fatigue, pain, nausea, anxiety and cognitive problems among others (25).

Using this assessment tool, it has been shown that children actively undergoing chemotherapy have a lower QOL than healthy children (26) or even those 1 year removed from chemotherapy (27). Additionally, researchers have measured the changes in patient QOL over the course of ALL therapy. In patients with SR-ALL or HR-ALL, nausea, procedural and treatment anxiety and worry were worse during induction compared to maintenance therapy (28). Another similar study demonstrated a lower health-related QOL in patients in induction therapy compared to all other phases of treatment (29).

Little research has been performed to analyze the effect of physical activity on QOL in ALL patients undergoing chemotherapy. One randomized trial demonstrated improved QOL in pediatric cancer patients, including those with ALL, who participated in physical activity sessions during hospitalization (30). In adolescent survivors of ALL, leisure-time physical activity was also associated with improved QOL (31). Greater research is needed to better understand the ability of physical activity, and dietary intervention, to improve patient QOL during and after chemotherapy.

2.6 STUDY SIGNIFICANCE

To our best knowledge, no clinical study has reported the effect of a combined diet and activity program as an adjuvant to chemotherapy in overweight and obese pediatric patients with any cancer diagnosis. However, with the combined expertise of our integrative medicine team of dieticians, physical therapists, oncologists and endocrinologists, we are confident that a comprehensive obesity-targeted intervention will reduce fat gain and lean muscle loss to improve treatment efficacy and QOL during therapy. The intervention will have the added benefit of promoting healthier lifestyle choices throughout the rest of treatment and into adulthood.

3.0 PRELIMINARY DATA

Obesity is a common problem in our patients with ALL.

In our cohort of adolescents with HR-ALL at CHLA, 48% were overweight or obese at diagnosis. Further, from the time of diagnosis to the end of the induction phase, subjects had an ~25% increase in body fat over these first 28 days of chemotherapy alone (from $23.3 \pm 9.1\%$ at time of diagnosis to $33.7 \pm 9.8\%$ at end of induction, $p < 0.001$, Fig. 1). Even more striking, this gain in body fat percentage was present in the entire cohort regardless of starting body composition (Fig 1.). Body fat then increased even further, to a mean of $37.1 \pm 7.9\%$ by the end of Delayed Intensification, following approximately seven months of intensive chemotherapy ($p < 0.001$, not shown). Overall, this increase in body fat represents a gain of 5.2 ± 4.9 kg of adipose tissue over the entire study period. Given our findings that adipose tissue can directly impair chemotherapy efficacy on ALL (32,33), this gain in body fat during such the critical chemotherapy dose-intensive treatment period is very concerning.

[figure not shown]

Fig 1. Body fat percentage measured by DXA scan in 10-21 year old children at diagnosis and end of induction. *** $p < 0.001$

Obesity impacts ALL survival within the first month of treatment. Treatment for childhood ALL generally lasts for 2-3 years. The first month of treatment (induction) is intense including prolonged high doses of steroids, and weekly chemotherapy, and frequent physician visits. Response to induction therapy through clearance of leukemia from the bone marrow as measured by flow cytometry and reported as “minimal residual disease” (MRD) is generally accepted as one of the best predictors of long-term survival (34). Given the association observed between obesity at diagnosis and EFS (1), we examined whether weight status at diagnosis would increase the risk of residual leukemia at the end of induction as measured by MRD. To do this, we retrospectively evaluated the records of 198 children treated at CHLA for B-precursor ALL. We observed that MRD positivity (as defined per COG by MRD with multicolor flow cytometry $\geq 0.01\%$) was increased in children who were overweight or obese (Fig 2 above).

The strongest association was in obese patients, who had a statistically and clinically significant higher risk of persistent MRD (Odds ratio 2.5, 95% CI 1.2 – 5.1, $p = 0.014$, adjusted for NCI risk group and validated leukemia risk factors) but with increased risk present in the overweight too (OR 1.37, $p=0.046$ for the three weight-group analysis). Evaluation of BMI percentile as a continuous variable further confirmed increased prevalence beginning in the overweight range (Fig. 2). Thus, the effect of overweight and obesity to worsen EFS is present during Induction.

[figure not shown]

Fig 2. BMI percentile and MRD positivity ($\geq 0.01\%$).

The effects of obesity are reversible. As weight is not static during ALL therapy (10), we recently evaluated the effect of duration of exposure to extreme weight on survival (Fig. 3, 35). In a retrospective COG study led by [name] et. al., in 2,008 children with HR-ALL, we determined that while children who were obese for greater than 50% of the early intensive chemotherapy phase had a poorer event free survival (HR of event = 1.43 [1.04-1.96] compared to those of “normal” weight), obese children whose weight normalized out of the obese range for more than 50% of the time of early intensive therapy had an improved outcome similar to those never obese (HR = 0.99 [0.62-1.58]). These data suggest the effect of obesity might be reversible.

[figure not shown]

Fig 3. EFS per BMI during HR-ALL Therapy

[figure not shown]

Fig 4. Diet affects ALL survival. Dieted mice were switched to 10% fat diet on day 7, when vincristine (VCR) treatment was initiated.

Remarkably, obese mice switched to a low fat diet had a substantially improved survival compared to the non-switched animals ($p<0.001$), and even survived longer than controls that had been raised on the low fat diet ($p<0.01$, Fig 4). Thus, switching mice from high fat to low fat diet when treatment is started substantially improves leukemia survival.

Obesity increases toxicity. As part of the same COG described above ([name] et. al.), we also evaluated obesity as an ongoing risk for toxicity. In doing so, we found a striking effect of obesity on toxicity within each phase of pediatric ALL chemotherapy for children with HR-ALL: in 2,008 children (representing 13,946 cycles of chemotherapy), obesity was associated with increases in hepatic ($OR = 1.32$ [1.15-1.51], $p<0.001$) and pancreatic ($OR = 1.53$ [1.22-1.92], $p<0.001$) toxicity within each cycle of chemotherapy as compared to lean or underweight children. Toxicity affecting the liver and pancreas are specifically

To address this important question, we designed experiments to determine whether or not dietary intervention that was initiated when leukemia is diagnosed could improve outcome. Diet-induced obese (DIO) mice and matched controls were transplanted with ALL cells and chemotherapy with vincristine (VCR) was initiated 7 days after transplant, as previously described (32). At this point, half of the obese mice were switched to a low (10%) fat diet. Thus, this experiment simulated the clinical condition in which a dietary intervention could be initiated at the time of diagnosis, namely at the same time that chemotherapy would be started.

Remarkably, obese mice switched to a low fat

notable in ALL regimens as they limit our ability to deliver optimal dosing of chemotherapy. Of note, and germane to the secondary objectives of this proposal, obese children also suffered from reduced strength during therapy (OR = 1.33 [1.08-1.64], p<0.001) as compared to those lean/underweight. Healthy reduction in body fat therefore has significant potential to not only improve survival, but to reduce key toxicities during ALL therapy.

Physical activity can be targeted in ALL. In a recent pilot study on preferences for physical activities and engagement in children and adolescents with ALL, we assessed 37 patients ages 10-18 (68% male; 65% Latino) using the Activity Preferences and Participation Scale (APPS), a newly developed measure designed to identify activity preferences, activity frequency, and social engagement in activity. The tool was administered on an iPad, and included perceptions of activity levels, self-reported changes in activity levels since diagnosis, and perceived barriers to engaging in physical activity and the importance of physical activity. Of the participants, 14 were in the induction/consolidation phase of treatment, 12 in Maintenance, and 11 off-treatment. Forty percent of individuals in the sample were overweight or obese. At all phases of treatment, participants strongly preferred and participated in sedentary activities. There was a high correlation between activity preference and activity participation in moderate-vigorous activities. Of particular relevance to the present study is that more than half of the participants in the induction/consolidation phase stated that fatigue, poor balance or weakness, and energy levels were barriers to participation in physical activity, while approximately 1/3rd reported that feeling sick or nauseated was a barrier. Most participants reported being less physically active since they were diagnosed with ALL, with the greatest declines reported in the induction/onsolidation (100%). All participants reported that they would like to be more physically active. As would be anticipated, induction chemotherapy fosters a non-active lifestyle; an integrative medicine intervention educating subjects and families how to safely exercise is both urgently needed and desired by families.

4.0 SCREENING AND ENROLLMENT

4.1 SUBJECT IDENTIFICATION

Physicians who wish to enroll patients should first contact the local site's research coordinator to determine if the study is currently open to accrual. Patients with newly diagnosed HR-ALL greater than or equal to 10 years of age are to be identified for eligibility screening by the oncology care team and/or study investigators. Screening logs with a coded identifier are to be maintained by each site; for eligible subjects not enrolled, the reason should be recorded.

4.2 IRB APPROVAL

Local IRB approval at each site must be confirmed by the research coordinator prior to enrolling a patient.

4.3 SCREENING PROCEDURES

Studies or procedures performed solely for clinical indications (and not done for purposes of determining study eligibility) may be used to screen for initial study eligibility and thereafter may be used for baseline values even if the studies were done before informed consent was obtained.

Diagnostic or laboratory studies performed exclusively to determine eligibility for this trial must only be done after obtaining written informed consent.

4.4 INFORMED CONSENT/ASSENT

Potential subjects and/or their parent(s) or guardian(s) (as applicable) will have the following carefully explained as described in the IRB-approved consent/assent documents: (1) the investigational nature of the research, (2) the objectives of the research, (3) the procedures involved in the research, and (4) any and all risks and discomforts due to participation. Clarification questions will then be elicited from the potential subject and/or their parent(s) or guardian(s). Only afterwards will an informed consent and assent document be signed as per institutional guidelines, with a copy to be given to the patient and the original placed in the research record.

Study participants are to be consented by the study investigators during their routine comprehensive study consent conference and/or by study investigators. As is the departmental standard practice regarding opening and accruing patients to clinical trials, care teams are to be fully briefed about the study details prior to study opening and will have the opportunity to ask clarifying questions. In addition, care teams will be kept apprised of any developments in study operation over the course of the study. Study investigators will also be available at all times to clarify any questions prior to the consent conferences.

4.5 CONTACT REQUIREMENTS

After eligibility requirements are met as per below, the principal investigator should be notified via email of subject eligibility and enrollment status.

4.6 ELIGIBILITY CHECKLISTS

The “Eligibility Checklist” must be completed, signed, and dated by the clinical research coordinator (or study investigator) prior to official study enrollment. This form must then be maintained in the study record.

4.7 STUDY ENROLLMENT

Once all applicable eligibility requirements are met, the patient will be enrolled in the study by the research coordinator.

Timing of Enrollment: Patients will ideally be enrolled prior to starting systemic chemotherapy (not including steroid pre-treatment/steroid prophase) but must be enrolled within 24 hours of starting systemic chemotherapy. Enrollment after 24 hours of starting systemic chemotherapy will be allowed at the discretion of the PI (or delegate) through the end of “chemotherapy day” 4.

4.8 PATIENT REGISTRATION

After subjects have been enrolled on the study, the **coordinating center (CHLA) will assign a unique study identifier to be emailed to each site.** Thereafter, they will be identified only by this unique identifier. All medical information will be protected as per the section below on “Records and Reporting.”

5.0 PATIENT CRITERIA FOR ELIGIBILITY

The eligibility criteria listed below are to be interpreted literally. All clinical and laboratory data required for determining eligibility of a patient enrolled on this trial must be available in the patient's medical and research record which will serve as the source document for verification at the time of audit.

5.1 INCLUSION CRITERIA

Subjects:

- Are greater than or equal to 10 years of age and less than or equal to 21 years of age at time of diagnosis
- Have a new diagnosis of untreated NCI/Rome High Risk B-precursor ALL (HR-ALL)
- (with the exception of steroid pre-treatment/steroid prophylaxis or the administration of intrathecal chemotherapy)
- Are beginning treatment on- or as per- a CCG-COG¹ protocol with a 4-drug Induction including vincristine, daunorubicin (or doxorubicin), asparaginase, and at least 14 days of glucocorticoid steroids

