9.1 REQUIRED OBSERVATIONS

“At Diagnosis” blood samples should be collected before or in closest proximity as possible to starting systemic chemotherapy (steroid pre-treatment, steroid prophylaxis, or intrathecal therapy may have already been given), but all samples must be collected before the start of the activity/nutrition intervention and prior to the end of chemotherapy day 4

The DXA scan should be done in closest proximity to diagnosis as is feasible, but **must be done within 96 hours from the beginning of systemic chemotherapy** and ideally before the start of the activity/nutrition intervention. The timing of the DXA scan in relation to chemotherapy and the intervention will be recorded.

STUDY MEASURE		Diagnosis (Day 1)	Day 8	Day 15	Day 22	End Induction (Day 29)	Start IM#1	Start Maint
Patient History	Clinical History ^{1*}	X	X	X	X	X	X	X
Anthropo-metrics	Height/Weight*	X	X	X	X	X	X	X
	Tricep skin folds	X	X	X	X	X	X	X
	Waist to hip ratio	X	X	X	X	X	X	X
Clinical Assessments	RD Assessment-3 day food log	X				X		
	RD Assessment-24 hr recall	X	X	X	X	X	X	X
	PT Assessment-Complete BOT2	X				X		
	PT Assessment-BOT2 –Brief		X	X	X		X	X
	Fitbit Tracker	Continuous from time of study entry until study end						
Laboratory Tests (blood) ²	Liver function tests ^{3*} (AST/ALT/Bili)	X	X	X	X	X		
	Lipid Panel	X				X	X	X
	[name] Labs	X				X	X	X
	Peripheral blood leukemia blasts ⁴	X						
	Pregnancy Test*	X				X		
Pathology Tests	Bone Marrow Aspirate ^{5*}	X				X		
	Biopsy Marrow Biopsy ⁵	X*				X		

Radiology Tests	DXA Scan	X				X ⁶		
Survey Instruments ⁷	PedsQL - Core	X				X	X	X
	PedsQL - Fatigue	X				X	X	X
	CASP	X				X	X	X

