*Indicates test per Standard of Care (SOC). ¹ Clinical History includes any time NPO, any use of nasogastrintestinal (NG) or nasojejunal (NJ) nutrition, any parenteral nutrition, any surgeries, any ICU admissions, Grade 3 or 4 hepatic or pancreatic toxicity, presence of osteonecrosis or fracture. ²Research laboratories to include IGF-1 and obesity-related interleukins/signaling factors, leptin, adiponectin. Peripheral blood will not be collected in patients who are Jehovah Witness or with a medical contraindication. ³ Will record if collected routinely per SOC. Each visit ± 3 days. End of induction includes any time prior to start of Consolidation phase. If Grade 3 hepatic toxicity during induction, will record values with date of resolution through start of IM#1 (<grade 2). ⁴To be collected in those with a circulating absolute blast count $\geq 500/\mu\text{L}$. ⁵Extra aspirate for research will be collected as per below only if sufficient specimen is available; only specimens from bone marrow biopsies processed in saline will be collected for study. ⁶End of induction scan to be done between days 29 and 36 of therapy in as close proximity to day 29 as possible and prior to any subsequent systemic chemotherapy. ⁷Available in Spanish and English; if subject does not speak either, will be administered in an assisted manner using in-person or phone-based medical interpreters.

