13.2 PRIMARY ENDPOINT EVALUATION

The primary endpoint for efficacy is a reduction in gain of body fat percent (per DXA) from diagnosis to the end of induction. From data on 36 patients from the historical cohort at CHLA with DXA scans pre and post induction, there was a significant average fat gain during induction therapy of 5.5 ± 3.3 percent (mean \pm s.d.), $p < 0.001$. Based on a two-sample (36 historical, 36 present study) two-sided t-test with 5% Type I error, there will be at least 90% power to detect a 2.5 percentage point reduction in change in body fat as a result of intervention (e.g. from gain of 5.5 to a gain of 3.0%). Hence, this study has sufficient power to detect subtle, achievable effects on body fat during induction, and will with certainty detect stabilization of or a decrease in body fat during induction.

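### Steroid exposure, a driver of fat gain that the protocol itself names, is neither a listed study observation nor part of the primary comparison with historical patients

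*Combined protocol and SAP*

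**What the plan says.** - **Eligibility (Section 5.1).** Treatment must be on, or as per, a CCG-COG protocol with "a 4-drug Induction including vincristine, daunorubicin (or doxorubicin), asparaginase"; the steroid requirement reads "asparaginase, and at least 14 days of glucocorticoid steroids". No agent, dose or maximum duration is given. Patients must be untreated, "with the exception of steroid pre-treatment/steroid prophylaxis or the administration of intrathecal chemotherapy"; the amount of such pre-treatment is not fixed.
- **Steroid and the outcome (Section 2.2).** "The use of glucocorticoids such as dexamethasone and prednisone during induction therapy likely contribute to this fat gain". The same paragraph also points to inactivity and to dietary changes caused by steroids.
- **Required observations (Section 9.1).** Footnote 1 begins "Clinical History includes any time NPO" and goes on to tube feeding and "any parenteral nutrition, any surgeries, any ICU admissions, Grade 3 or 4 hepatic or pancreatic toxicity, presence of osteonecrosis or fracture". Neither this footnote nor any row of the schedule lists steroid agent, dose or days. Scan timing is covered: "The timing of the DXA scan in relation to chemotherapy and the intervention will be recorded".
- **Primary comparison (Section 13.2).** The control figure comes "From data on 36 patients from the historical cohort at CHLA with DXA scans pre and post induction": a mean gain of 5.5 points with SD 3.3. The test is a two-sided, two-sample t-test at 5%, 36 against 36, with no covariate named. Covariate adjustment is mentioned only for the MRD analyses in Section 13.3, and steroid is not named there.
- **Sites (Section 13.1).** Outside sites joined at AMD03. The historical DXA patients are all from CHLA.

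**The concern.** The primary comparison is not randomised, so its credibility depends on the two cohorts being alike in whatever else moves body fat during induction. The protocol identifies steroid as one such factor, lets it vary among study subjects above a floor, and does not say what the historical patients received. Practice could differ by calendar period, or between CHLA and the added sites.

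If exposure does differ, the difference enters the estimated intervention effect directly. Lower exposure in study subjects would look like a benefit; higher exposure would mask one. As the plan stands, a reader of the results would have no planned table or analysis with which to judge either possibility.

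**Working it through.** **Inputs from Section 13.2.** 36 per group; SD 3.3; two-sided alpha 0.05; target reduction 2.5 points; historical gain 5.5 points.

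**Step 1: reproduce the stated power.** SE = 3.3 × √(1/36 + 1/36) = 0.778. Standardised effect = 2.5 / 0.778 = 3.21. Power is 0.895 by the normal approximation and 0.887 by the noncentral t on 70 df. Both are close to the plan's figure of at least 90%, and marginally below it.

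**Step 2: the difference that is just significant.** The critical t on 70 df is 1.994, so an observed difference of 1.994 × 0.778 = 1.55 points suffices. That is 1.55 / 5.5 = 28% of the historical gain. A confounding shift of that size alone would give a significant result about half the time.

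**Step 3: an illustrative range of bias.** The documents give no steroid course for the historical cohort and no relation between exposure and gain, so these are assumptions:
- every historical patient had a 28-day course;
- gain is proportional to steroid days, so a 14-day course gives 5.5 × 14/28 = 2.75 points, a drop of 2.75;
- 10%, 25% or 50% of study subjects had the 14-day course.

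Bias = share × 2.75 = 0.28, 0.69 or 1.38 points. Other assumptions lead to the same values. For example, half the subjects with a 25% smaller gain gives 0.5 × 0.25 × 5.5 = 0.69.

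**Step 4: consequence in each direction.** With noncentrality = shift / 0.778 and 70 df, the upper-tail probability of significance is taken at a shift equal to the bias (inert intervention, bias favouring the study group), and at a shift of 2.5 minus the bias (true effect of 2.5 points, bias against the study group).

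| Bias (points) | Inert intervention: chance of a significant benefit | True 2.5-point effect, bias against it: power |
|---|---|---|
| 0 | 2.5% | 89% |
| 0.28 | 5.4% | 81% |
| 0.69 | 13.8% | 63% |
| 1.38 | 41% | 30% |

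The 0 row is also the result when both cohorts have the same steroid mix, whatever that mix is.

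**The case against.** Four points can fairly be made for the plan.

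1. **The backbone is restricted.** A reader might infer that any induction qualifies. It does not: Section 5.1 requires a CCG-COG four-drug regimen, and Section 12.2 takes a subject off study if a changed induction plan no longer meets eligibility. This stands. It narrows the variation but does not remove it, because differences above the 14-day floor remain eligible.

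2. **The exposure is retrievable.** A reader might infer that an imbalance could never be detected. Section 5.0 requires the data that establish eligibility to be in the medical and research record, so the planned course should be documented. Footnote 1 says what the clinical history includes, and the case report forms are not among the documents, so they may capture more. This stands as well. What is missing is a stated requirement to collect the course actually given, the same information for the historical patients, and an analysis that uses it.

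3. **No imbalance is shown.** A reader might infer that study subjects had shorter courses than the controls. No section gives the historical agent, dose or days. The control group is described in Section 6.1 as recent, and the preliminary CHLA data in Section 3.0 concern a similar age range and the same disease. With no cap on duration and with pre-treatment allowed, a difference could equally run towards more exposure in study subjects. This stands in full.

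4. **The proportional model is crude.** It attributes the whole 5.5-point gain to steroid days, whereas Section 2.2 says only that steroids likely contribute and also names inactivity and diet. It ignores agent and dose. This stands, so the table shows how sensitive the test is to a shift of a given size; it does not predict that shift.

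**Conclusion.** The concern holds in limited form and calls for a cheap improvement. Steroid exposure may vary under the eligibility rule, is not listed as a study observation, is undescribed for the controls, and is absent from the primary analysis. An imbalance, if there is one, would be confounded with the intervention and could create or hide a benefit.

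The documents do not establish that an imbalance exists, nor its size or direction. The figures above rest on the assumed 28-day historical course, proportionality to days and the assumed shares. The part that needs none of these is that a shift of about 1.55 points is enough to reach significance at 36 against 36. Nothing here supports reading the primary comparison as already biased, or the steroid data as beyond recovery.

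**What to change.** - **Section 9.1, Clinical History:** add steroid agent, dose, start and stop dates, and cumulative prednisone-equivalent dose from the first dose (including pre-treatment) to the Day 29 DXA, taken from the medication record.
- **Historical cohort:** abstract the same items for the 36 patients with DXA scans.
- **Section 13.2:** report both distributions side by side, and pre-specify a sensitivity analysis of the primary endpoint limited to study and historical patients with the same planned steroid agent and duration. Fixing this before results are seen avoids choosing the subset afterwards.

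The cost is one case report form page per subject, 36 chart abstractions and one further analysis. The restricted analysis will have fewer patients and so lower precision; it should be read as a check on the primary result. No patient procedure is added, and no change to eligibility or treatment is proposed.
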